3.5. Methods of Pooling Data

Data will be summarized separately for each dose group (i.e., dose level and regimen). Data from expansion cohorts that are dosed at the same level and regimen as a previous cohort will be pooled with the previous cohort for presentation by dose group. In addition, safety data will be presented overall.

Data will be tabulated separately for dose groups dosed 4 weeks apart and dose groups dosed 3 weeks apart, if applicable.

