#### 1.6.1 Infusion-Related Reactions

Infusion-related reactions can occur with systemic administration of certain biological agents such as liposomes or monoclonal antibodies. These may include acute reactions or delayed febrile reactions. Premedicating patients with corticosteroids and/or antihistamines, or slowing of the infusion rate, are approaches that have been taken to reduce the incidence and/or severity of IRRs. Consistent with this, a premedication regimen (dexamethasone or equivalent, paracetamol or equivalent, histamine H1/H2 receptor antagonist [H1/H2 blocker]) similar to that proposed for this study was used in the prior ALN-PCS02 and ALN-TTR01 clinical studies that employed siRNAs in LNP formulations (Section 1.3).

In order to reduce the potential for an IRR with ALN-TTR02, all patients in this study will be premedicated prior to dosing with ALN-TTR02. The premedication regimen will include dexamethasone (or equivalent), paracetamol (or equivalent), and H1 and H2 blockers (as described in Section 5.5). The infusion rate of 1 hour or longer will also help to reduce the potential for acute IRRs. The suggested clinical course for managing IRRs is provided in Section 5.11 and in Appendix 1 and Appendix 2.

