#### 5.6 Dose, Route, and Schedule of Study Drug Administration

Consented patients meeting the eligibility criteria will be enrolled into sequential cohorts of increasing doses of ALN-TTR02. Each cohort will consist of 3 patients.

Study drug will be administered under the supervision of the Investigator or designee. Study drug doses will be administered as a 60-minute IV infusion (flow rate of approximately 3.3 mL/min) 4 weeks apart. The dosing of ALN-TTR02 in the optional cohorts will be once every 4 weeks for the first optional cohort and once every 3 or 4 weeks for the remaining 4 optional cohorts, at a dose previously determined by the SRC to be safe and tolerable. Study drug will be administered via a controlled infusion device

with an extension set containing a 1.2 micron filter supplied by Alnylam or designee. Infusion products containing polyvinyl chloride, di(2-ethylhexyl)phthalate (PVC, DEHP) must NOT be used. For patients enrolled in an optional cohort evaluating the alternative premedication regimen, the flow rate will be approximately 1.1 mL/min during the first 15 minutes (1/3rd the original flow rate) with the remainder of the infusion taking place over 55 minutes (at a flow rate of approximately 3.3 mL/min) for a total infusion time of approximately 70 minutes.

The patient's infusion site will be checked pre-dose, during infusion, and after infusion for any safety concerns (e.g., infusion-associated reactions). The infusion time may be extended up to 3 hours in the event of a mild or moderate infusion reaction (study drug administration will not be resumed for any patient following a severe infusion reaction). Patients will remain hospitalized at the study site for at least 24 hours following completion of dosing on Day 0 and Day 28 to be observed for safety assessments and PK sampling.

The planned study drug doses are 10, 50, 150, and 300 µg/kg.

Subjects who weigh 105 kg or more will receive ALN-TTR02 dosing based on an assumption of a body weight of 104 kg.

Prior to administration of the second dose of ALN-TTR02, the inclusion and exclusion criteria must be reassessed to ensure that the patient still qualifies for participation in the study.

The planned study drug doses and patient cohorts are identified in Table 5-1. Dose escalation procedures are described in Section 5.7.1.

Patient Cohort	ALN-TTR02 Dose (μg/kg)	Initial Enrollment	Total Enrollment a
1	10	3	Up to 27 patients
2	50	3	
3	150	3	
4	300	3	

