**Planned Dose Cohorts and Enrollment Table 5-1:** 

#### 5.7 Criteria for Dose Escalation, Dose Modification or Discontinuation of **Study Drug**

#### 5.7.1 **Dose Escalation Procedures**

The initial dose of ALN-TTR02 is 10 µg/kg. Dose escalation to 50, 150, and 300 µg/kg is planned.

Within each of the cohorts, the first patient will receive their first dose and if the dose is well tolerated, per Section 5.7.3 (Dose-limiting Toxicity), Patients 2 and 3 will receive their first dose at that same dose level no sooner than 48 hours apart, with Patient 2 receiving a dose of study drug no sooner than 48 hours after the dosing of Patient 1. Similar to the first dose, the second dose will be administered to patients 4 weeks after the first dose in a sequential manner with at least 48 hours separating dosing of each patient. If after the first dose, ALT and AST are > 2.5 x ULN, that patient would not receive their second dose. Dose escalation to the next cohort will proceed after the collective safety and tolerability data through at least 96 hours post-first dose from the 3 patients in the previous cohort has been reviewed by the SRC. If the administered dose is found to be safe and well tolerated, dosing for the next cohort will begin no sooner than 96 hours after Patient 3 has safely received dose 1 from the previous cohort. Patients in the cohort would be dosed and reviewed for safety and tolerability following the same procedures as used for other cohorts (as stated above).

Up to 5 optional cohorts may be included to confirm the safety, tolerability, and/or PD effect of previously evaluated dose levels, which may include evaluation of the original dosing regimen (once every 4 weeks), an alternative dosing regimen (once every 3 weeks), and/or an alternative premedication regimen and infusion rate at a specific dose of ALN-TTR02. Dosing in these optional cohorts may occur at a previously tested dose that was found to be safe and where stopping rules were not met or at an intermediate dose level. Each optional cohort will be comprised of 3 patients.

For patients on all dose levels other than the starting dose level of  $10 \mu g/kg$ , prior to receiving the second dose the SRC will review the cumulative safety and tolerability data of at least 2 patients from the previous dose level(s) with at least 96 hours of follow-up after receiving a second dose of study drug.

The dosing of patients within each of the first 4 cohorts is depicted in

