3.2. General Methods

All data listings that contain an evaluation date will contain a relative study day. Pre-treatment and on-treatment study days are numbered relative to the day of study medication dosing, which is designated as Day 0. For example, the day prior to study medication will be Day -1 and the day after study medication will be Day 1.

All output will be incorporated into Microsoft Word or Excel files, or Adobe Acrobat PDF files, sorted and labeled according to the International Conference on Harmonisation (ICH) recommendations, and formatted to the appropriate page size(s).

Tabulations will be produced for appropriate demographic, baseline, efficacy, and safety parameters. For categorical variables, summary tabulations of the number and percentage of subjects within each category (with a category for missing data) of the parameter will be presented. For continuous variables, the number of subjects, mean, median, standard deviation (SD), minimum, and maximum values will be presented.

All data will be presented in by-subject data listings.

As this is a Phase 2 dose-escalation trial, formal statistical hypothesis testing will not be performed. Although exploratory confidence intervals (CIs) will be presented as described below, no formal statistical conclusions will be made based on these estimates.

Subjects will be analyzed in the cohort to which they were originally assigned. Data will be tabulated for each dose group (i.e., dose level, regimen, and pre-medication regimen).

Laboratory data collected and recorded as below the limit of detection will be set equal to the lower limit of detection for the calculation of summary statistics.

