Figures will be produced for each dose group that display each subject's AST, ALT, alkaline phosphatase, and bilirubin (total and direct) results over time; 1 figure will be produced for each dose group and liver function test parameter, with lines presenting subject results over time. In addition, treatment group means, with standard error bars, will be plotted over time. Similar plots will be produced for complement factor (Bb) and cytokines. A vertical reference line will identify the nominal Dose 2 dosing day (i.e., Day 28 for the 4-week regimen or Day 21 for the 3-week regimen).

Urinalysis results will be included in subject listings but will not be included in summary tables.

Tryptase and C3a will be included in subject listings for any subjects experiencing an IRR.

Results of anti-PEG antibody testing will be listed if any positive results are reported.

All laboratory data, including the Day 0 fasting lipid panel, will be provided in data listings.

Laboratory values outside of the normal ranges will be listed separately, together with comments as to their clinical significance.

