Table 14.2.3.3A	Summary of Percent Reduction in Serum Mutant TTR (LCMS/MS) by Dose Group – Q4W Cohorts (Intent-to-Treat Analysis Set – V30M Subjects)
Table 14.2.3.3B	Summary of Percent Reduction in Serum Mutant TTR (LCMS/MS) by Dose Group – Q3W Cohorts (Intent-to-Treat Analysis Set – V30M Subjects)
Table 14.2.4.1A	Summary of Area under the TTR (ELISA) Concentration Time Curve – Q4W Cohorts (Intent-to-Treat Analysis Set)
Table 14.2.4.1B	Summary of Area under the TTR (ELISA) Concentration Time Curve – Q3W Cohorts (Intent-to-Treat Analysis Set)
Table 14.2.4.2A	Summary of Area under the Wild Type TTR (LCMS/MS) Concentration Time Curve – Q4W Cohorts (Intent-to-Treat Analysis Set – V30M Subjects)
Table 14.2.4.2B	Summary of Area under the Wild Type TTR (LCMS/MS) Concentration Time Curve – Q3W Cohorts (Intent-to-Treat Analysis Set – V30M Subjects)
Table 14.2.4.3A	Summary of Area under the Mutant TTR (LCMS/MS) Concentration Time Curve – Q4W Cohorts (Intent-to-Treat Analysis Set – V30M Subjects)
Table 14.2.4.3B	Summary of Area under the Mutant TTR (LCMS/MS) Concentration Time Curve – Q3W Cohorts (Intent-to-Treat Analysis Set – V30M Subjects)
Table 14.3.1.1	Summary of Treatment-Emergent Adverse Events, Overall and by Dose Group (Intent-to-Treat Analysis Set)
Table 14.3.1.2	Treatment-Emergent Adverse Events, Overall and by Dose Group (Intent-to-Treat Analysis Set)
Table 14.3.1.3	Treatment-Emergent Adverse Events Related to Study Drug, Overall and by Dose Group (Intent-to-Treat Analysis Set)
Table 14.3.1.4	Severe Treatment-Emergent Adverse Events, Overall and by Dose Group (Intent-to-Treat Analysis Set)
Table 14.3.1.5	Severe Treatment-Emergent Adverse Events Related to Study Drug, Overall and by Dose Group (Intent-to-Treat Analysis Set)
Table 14.3.1.6	Serious Treatment-Emergent Adverse Events, Overall and by Dose Group (Intent-to-Treat Analysis Set)
Table 14.3.1.7	Treatment-Emergent Infusion Related Reaction Signs and Symptoms, Overall and by Dose Group (Intent-to-Treat Analysis Set)
Table 14.3.1.8	Most Common ($\geq 10\%$ of All Subjects) Treatment-Emergent Adverse Events, Overall and by Dose Group (Intent-to-Treat Analysis Set)
Table 14.3.1.9	Treatment-Emergent Adverse Events by Maximum Relationship to Study Drug, Overall and by Dose Group (Intent-to-Treat Analysis Set)
Table 14.3.1.10	Treatment-Emergent Adverse Events by Maximum Severity, Overall and by Dose Group (Intent-to-Treat Analysis Set)
Table 14.3.2.1	Subject Listing of Deaths

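### SAP 3.2 and SAP 3.5 define dose group differently, so cohorts on different premedication may be kept apart or merged in the safety tables

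*SAP*

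**What the plan says.** SAP 3.2 (General Methods): "Data will be tabulated for each dose group (i.e., dose level, regimen, and pre-medication regimen". That is three factors.

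SAP 3.5 (Methods of Pooling Data): "Data will be summarized separately for each dose group (i.e., dose level and regimen". That is two factors, and the rule that follows uses the same two: "Data from expansion cohorts that are dosed at the same level and regimen as a previous cohort will be pooled with the previous cohort". A later sentence of 3.5 adds that groups dosed 4 weeks apart and 3 weeks apart are tabulated separately. SAP 4.3.1 determines the group nadir for each combination of dose and regimen, again without naming premedication.

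The protocol makes overlap possible. Section 5.7.1: "Up to 5 optional cohorts may be included to confirm the safety, tolerability, and/or PD effect of previously evaluated dose levels". Section 5.7.2 anticipates that the first two optional cohorts keep the original premedication, and that the other three may use the alternative premedication and infusion rate. Section 5.6 ties the slower start to the alternative premedication: "For patients enrolled in an optional cohort evaluating the alternative premedication regimen, the flow rate will be approximately 1.1 mL/min" for the first 15 minutes.

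**The concern.** Both SAP sections introduce their list with i.e., so each claims to define the same term. They give different answers for cohorts that share dose and interval but differ in premedication. The SAP does not say which section prevails.

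Many safety tables are laid out by dose group, for example Table 14.3.1.7: "Treatment-Emergent Infusion Related Reaction Signs and Symptoms, Overall and by Dose Group (Intent-to-Treat Analysis Set". The same holds for the adverse event tables and the summaries of cytokines and CRP, complement Bb and serial vital signs. Their columns would depend on which section the programmer follows. Because the trial is open-label, the grouping could also be settled after the data have been seen.

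The factor at issue matters for tolerability. Protocol 1.6.1 says that premedicating patients, "or slowing of the infusion rate, are approaches that have been taken to reduce the incidence and/or severity of IRRs". The two regimens differ by design (protocol 5.5 and 5.6). The original is oral, given the evening before and again 30 to 60 minutes before a 60-minute infusion. The alternative is mainly intravenous, given on the day only, with an infusion of about 70 minutes. A merged infusion-reaction column would hide the contrast that those optional cohorts may be opened to explore.

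**Working it through.** **What regimen means in 3.5.** Three texts bear on it.
- SAP 3.2 lists regimen and premedication regimen as separate items, so there the first does not contain the second.
- SAP 4.5.3 attaches the word to the interval: "Day 28 for the 4-week regimen or Day 21 for the 3-week regimen".
- Protocol 5.7.1 and 5.7.2 use dosing regimen for once every 4 or once every 3 weeks, and list premedication apart from it.

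The most natural reading of 3.5 is therefore dose level plus interval.

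**Total enrolment (SAP 3.1).** 4 planned cohorts × 3 + 5 optional cohorts × 3 = 12 + 15 = 27, which reproduces the SAP's figure. No power calculation applies; SAP 3.1 says so.

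**Assumptions for column sizes.** Optional cohorts 1 and 2 use the original premedication, cohorts 3 to 5 may use the alternative, and no patient is replaced. Optional cohort 1 is dosed every 4 weeks; cohorts 2 to 5 are dosed every 3 or 4 weeks.

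- Patients on the alternative: at most 3 × 3 = 9, and 9/27 = 33%.
- Every 4 weeks at one dose: 3, 6 or 9 original (one planned cohort plus up to two optional) with 3, 6 or 9 alternative. Merged n runs from 3 + 3 = 6 to 9 + 9 = 18.
- Every 3 weeks at one dose: 3 original (optional cohort 2 only) with 3, 6 or 9 alternative. Merged n runs from 3 + 3 = 6 to 3 + 9 = 12.
- Alternative share of a merged column: lowest 3/(9 + 3) = 25%, highest 9/(3 + 9) = 75%.

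**How often the definitions disagree.** Suppose all five optional cohorts repeat one planned dose and the last three use the alternative. The intervals of cohorts 2 to 5 give 2⁴ = 16 patterns. The definitions agree only when cohort 2 is 4-weekly and cohorts 3 to 5 are all 3-weekly, so they differ in 15 of 16. This count falls if the optional cohorts are spread over several doses. Two examples:
- All optional cohorts every 4 weeks: 3.2 gives columns of 9 and 9; 3.5 gives one of 18.
- Cohort 1 every 4 weeks, cohorts 2 to 5 every 3 weeks: 3.2 gives 6 (4-weekly, original), 3 (3-weekly, original) and 9 (3-weekly, alternative); 3.5 gives 6 and 12.

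**Precision.** With zero events, the exact two-sided 95% upper limit is 1 − 0.025^(1/n): 70.8% at n = 3, 45.9% at n = 6, 33.6% at n = 9, 26.5% at n = 12 and 18.5% at n = 18. For the 95% intervals planned for percent change in TTR, the half-width is t(0.975, n − 1)/√n in SD units: 2.484 at n = 3, 0.769 at n = 9 and 0.635 at n = 12. In the second example, the 3-weekly groups of 3 and 9 become one group of 12.

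**The case against.** The strongest reply is that regimen in 3.5 may already include premedication. The SAP never defines the word on its own, and in 4.5.3 it is qualified by the number of weeks. If regimen in 3.5 meant only the interval, the later sentence separating 4-week from 3-week groups would be largely redundant. SAP 3.2 is also the more specific text, and a programmer following it would produce the separated columns. This makes 3.5 less than a plain instruction to merge. It does not remove the conflict: 3.2 lists the two terms separately, the protocol uses dosing regimen for the interval, and the later sentence fits the split into Q4W and Q3W tables in SAP 7.1. Even on the broader reading, 3.5 is ambiguous and needs the same edit.

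The effect is also conditional. An optional cohort must be opened, use the alternative premedication, and repeat both a dose and an interval already used with the original. Optional cohorts may instead use an intermediate dose. This stands.

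No formal conclusion depends on the grouping either. There is no hypothesis testing, and escalation and stopping decisions rest with the Safety Review Committee. Listings 16.2.5.1, 16.2.7.3 and 16.2.8.18 and the individual plots allow the split to be rebuilt. Table 14.4.3 and the infusion-duration summary would show the mix inside a merged column. This also stands, and it limits the weight of the point. Listings do not, however, replace a planned summary column.

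Finally, the counts above measure who could share a column. They do not show how far any reaction rate would move, and the documents give no figure from which that could be calculated.

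**Conclusion.** The inconsistency is real and should be fixed: two sections of one plan give different rules for the same term. On the natural reading of 3.5, original and alternative premedication cohorts at the same dose and interval would share a column in tables that serve the primary objective.

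The sizes derived above rest on the premedication sequence that the protocol only anticipates, and on no replacements. If no alternative cohort repeats a dose and interval used with the original premedication, the two definitions give identical columns. Overall safety columns are unaffected in every case. Any comparison between the two regimens would be small, non-randomised and descriptive. Confidence is high that the texts conflict; whether the conflict takes effect depends on which optional cohorts are opened.

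**What to change.** Use one definition of dose group in SAP 3.2 and 3.5 and carry it into the group-nadir wording of 4.3.1: dose level, dosing interval, and premedication with its infusion rate. Infusion rate should be named, since neither definition mentions it. Pool only cohorts that match on all three.

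Show these groups as separate columns in the safety summaries, for example Tables 14.3.1.1 to 14.3.1.10 and 14.3.5.6 to 14.3.5.9. State the same grouping for Tables 14.3.5.10 and 14.4.1, whose titles name no dose group. A supplementary column pooled across premedication can be kept where precision matters more, for example for TTR. Protocol 9.2 tabulates by dose level and SAP 5 reports no changes from the protocol, so SAP 5 should record the finer grouping.

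The cost is a few phrases and some table columns, with no new data and no change to conduct. The downside is smaller columns: under the assumptions above, 3 to 9 patients each where merging would have occurred. With zero events, the upper limits are 71% at n = 3 and 34% at n = 9, against 19% for a merged 18. The separate columns support description only.

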3.6. Adjustments for Covariates

No formal statistical analyses that adjust for possible covariate effects are planned.

3.7. Multiple Comparisons/Multiplicity

Multiplicity is not of concern for this Phase 2 study with a descriptive interpretation.

3.8. Subpopulations

Summaries of serial TTR will be presented by genotype (V30M versus other) and use of TTR stabilizer (tafamidis or diflunisal use versus none).

3.9. Withdrawals, Dropouts, Loss to Follow-up

Subjects who voluntarily withdraw are termed dropouts. Dropouts may be replaced following discussion with the Investigator and Sponsor.

Subjects who are withdrawn due to AEs during infusion of the ALN-TTR02 will not be replaced.

If a subject is withdrawn/withdraws, the discharge procedures should be performed and an early termination (ET) visit scheduled as follows:

- If a subject is withdrawn/withdraws prior to Day 56, then the Day 56 assessments should be completed;
- If a subject is withdrawn/withdraws after Day 56 and prior to Day 208, then the Day 208 assessments should be completed.

Data collected at an ET visit will be included in Day 56 or Day 208 tabular summaries. That is, the Day 28 summary will include actual observed values from Day 56 along with data collected from any ET visits prior to Day 56. Similarly, the Day 208 summary will include data from subjects completing the study, along with any data collected at ET visits between Day 56 and Day 208.

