3.11. Visit Windows

It is expected that all visits will occur according to the protocol schedule of assessments. All data will be tabulated per the evaluation visit as recorded on the CRF even if the assessment is outside of the window for that study visit. In data listings, the study day relative to Day 0 (day of first dose) will be presented.

Unscheduled visits will be included in data listings, but no assignment to a study visit will be made for the purpose of summary tabulations.

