4.3. Pharmacodynamic Evaluation

4.3.1. Total Serum TTR (ELISA)

Serial measurements and changes from baseline of serum TTR through Day 208 will be summarized for each scheduled time point using descriptive statistics. Percent change from baseline will also be summarized. Ninety-five percent CIs for percent change will be presented. An overall summary of percent reduction in TTR will include the maximum percent reduction per dose group, dose group means (SD) at individual and group nadirs (defined below), and dose group means (SD) at Day 28 and Day 56 (Day 21 and Day 42 for optional cohorts dosed every 3 weeks).

The individual nadir TTR value, defined as the lowest observed TTR value from Day 1 to the Day 28 premedication assessment (Day 21 for optional cohorts dosed every 3 weeks), will be

determined for each subject. The nadir value will be plotted for each subject, grouped by dose group. Dose group means will be indicated on the plot. The value of the percent reduction associated with the nadir will be plotted similarly. The nadir value from the Day 29 to Day 56 interval (Day 22 to Day 42 for optional cohorts dosed every 3 weeks) will also be determined and plotted.

The group nadir TTR value, defined as the lowest observed mean percent TTR reduction from baseline from Day 1 to the Day 28 premedication assessment (Day 21 for optional cohorts dosed every 3 weeks), will be determined for each dose/regimen group. The group nadir value will be plotted for each group, along with standard error bars. The group nadir value from the Day 29 to Day 56 interval (Day 22 to Day 42 for optional cohorts dosed every 3 weeks) will also be determined and plotted.

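### SAP 3.9 puts early-termination values into the Day 56 and Day 208 rows with no limit on timing, and labels the first of these the Day 28 summary

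*SAP*

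**What the plan says.** SAP 3.9 first sends ET data to the Day 56 or Day 208 tables. It then explains the first of these: "the Day 28 summary will include actual observed values from Day 56 along with data collected from any ET visits prior to Day 56". The Day 208 summary combines completers' values "along with any data collected at ET visits between Day 56 and Day 208".

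SAP 3.11 sets no analysis windows. It starts from the premise that "It is expected that all visits will occur according to the protocol schedule of assessments", and then provides that "All data will be tabulated per the evaluation visit as recorded on the CRF even if the assessment is outside of the window". Unscheduled visits are handled differently: they are listed, but "no assignment to a study visit will be made for the purpose of summary tabulations". The actual study day appears in listings.

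SAP 4.3.1 names, among its overall TTR results, "dose group means (SD) at Day 28 and Day 56" (Day 21 and Day 42 for the 3-weekly cohorts). For the serial measurements it adds that "Ninety-five percent CIs for percent change will be presented".

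The protocol schedule gives Day 56 a window of ±3 days and Day 208 a window of ±2 weeks. After withdrawal before Day 56, protocol 4.5.2 and 6.4 and SAP 3.9 ask for one ET visit with the Day 56 assessments. Footnote a of the schedules in both documents asks for both the Day 56 and the Day 208 visits.

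**The concern.** TTR is expected to fall after a dose and then recover, so a TTR value means little without its time since dosing. A row labelled Day 56 should hold values from about 28 days after the second dose in the 4-weekly cohorts. Under 3.9 it can also hold a value from any earlier day, including one taken after a single dose. The same applies to vitamin A and RBP at Day 56 and Day 208, and to haematology, chemistry, liver and thyroid tests at Day 56. Anti-PEG antibodies are also drawn at these visits but are outside the by-visit summaries: "Results of anti-PEG antibody testing will be listed if any positive results are reported".

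Such cases are foreseeable. Protocol 3.1 and 5.7.1 describe patients who will not receive a second dose, 4.5.1 allows withdrawal for an adverse event or a DLT, and 7.4.1 sets PK sampling for one-dose patients.

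Two further gaps follow from the same text. If a withdrawn patient has both an ET value and a scheduled Day 56 value, which footnote a makes possible, 3.9 does not say which one is tabulated. The documents also do not say whether moving to the extension study counts as an ET visit.

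**Working it through.** **Label.** The sentence before the faulty one names Day 56 and Day 208, and the faulty sentence fills its table with Day 56 values. Day 56 is plainly meant. Because 4.3.1 reports Day 28 and Day 56 as separate TTR results, the sentence taken literally names the wrong one.

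**How far a value can be displaced.**
- ET on Day 1, tabulated at Day 56: 56 − 1 = 55 days early (window ±3 days).
- ET on Day 57, tabulated at Day 208: 208 − 57 = 151 days early (window ±14 days).
- Rollover is allowed from 28 days after the last dose: Day 28 + 28 = 56 in 4-weekly cohorts, Day 21 + 28 = 49 in 3-weekly cohorts. Both are far from Day 208.

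**Group sizes.** The SAP's planned maximum reproduces: 4 × 3 + 5 × 3 = 27.
- Smallest group: one cohort, n = 3.
- Largest under SAP 3.5 (pooling by dose level and regimen): 3 + 5 × 3 = 18, if all optional cohorts are 4-weekly at one tested dose.
- If premedication also defines the group (SAP 3.2), with the anticipated 2/3 split of optional cohorts: 3 + 2 × 3 = 9 on the original regimen and 3 × 3 = 9 on the alternative.
- Replacement patients are not counted.

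**Effect of one value.** If one of n values differs by a gap g from what it would have been at the nominal visit, the mean shifts by g/n. The documents give no g, so a range of 0 to 80 points of TTR reduction is assumed.

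| Gap g (points) | n = 3 | n = 9 | n = 18 |
|---|---|---|---|
| 0 | 0 | 0 | 0 |
| 40 | 13.3 | 4.4 | 2.2 |
| 70 | 23.3 | 7.8 | 3.9 |
| 80 | 26.7 | 8.9 | 4.4 |

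The 70-point row is an illustration from figures in the documents. Lowering by 90% (protocol 1.3, Phase 1 healthy volunteers) leaves 10% of baseline; recovery to 80% of baseline is the follow-up threshold in footnote r; 80 − 10 = 70. Gaps near 0 are plausible at 10 and 50 µg/kg, because protocol 1.3 reports robust effects only from 0.15 mg/kg upward.

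**Confidence interval.** Assume a t-interval and n = 3 with two equal values and a third 70 points away. The SD is 70/√3 = 40.4, the standard error 40.4/√3 = 23.3, and the 95% half-width 4.303 × 23.3, or about 100 points.

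**The case against.** The case for leaving the rule alone has several parts.

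- **The label misleads no one.** Probably true of a careful programmer, but the correction is one word in a prespecified document.
- **The pooling rule is explicit and agrees with 3.11, which tabulates by CRF visit whatever the day.** That consistency is real, and a window for ET visits alone treats them more strictly than scheduled visits. However, 3.11 expects scheduled visits to keep to the schedule, whereas an ET visit happens whenever the patient leaves.
- **A window does not separate one-dose from two-dose patients.** This stands in part. A one-dose patient who attends the real Day 56 visit stays in the row. The window does remove every ET value taken before the second dose.
- **Dropping a value costs precision.** For the same SD, going from n = 3 to n = 2 widens the 95% half-width from 4.303/√3 = 2.48 SD to 12.706/√2 = 8.98 SD. That is a real cost. The narrower interval, though, describes a mixture of times.
- **The illustration is generous.** It combines healthy-volunteer data from a study that included 500 µg/kg, a dose not planned here, with a threshold that is not an expected Day 56 value. If the patient is replaced and both are kept, n = 4 and the shift is 70/4 = 17.5. This is why the result is given as a range starting at zero.
- **The study is descriptive.** There is no formal testing, individual TTR and liver-test profiles are plotted, shift tables do not use the Day 56 mean, and listings give the day. All of this limits the harm.
- **Rollover is partly covered.** Protocol 4.5 counts a patient as complete after both doses and procedures through Day 56. Rollover from Day 49 in 3-weekly cohorts, and the Day 208 row, remain unclear.

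**Conclusion.** The concern holds. SAP 3.9 is a stated rule, not a missing detail, and it can place values from a different time since dosing, or from before the second dose, in rows labelled Day 56 or Day 208. The Day 28 label contradicts the sentence before it.

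The size depends on two things the documents do not give: how many out-of-window ETs occur and how far their values lie from the nominal visit. The range in the table rests on one displaced value, an assumed gap of 0 to 80 points and no replacements. The direction depends on the ET day.

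The reach is limited to by-visit summary tables and the corresponding mean plots; 3.9 itself mentions only tables. The 3-weekly Day 21 and Day 42 TTR results are not affected. The point should be fixed, but it does not threaten the trial's safety conclusions. The footnote a conflict and the status of rollover are secondary, but both need resolving for the rule to be workable.

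**What to change.** In SAP 3.9:

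1. Replace Day 28 with Day 56 in the label.
2. Include an ET value in the Day 56 or Day 208 row only if its actual study day lies within that visit's protocol window and the patient has no scheduled value there.
3. Show every other ET value in a separate early-termination row and in listings at its actual day, in line with how 3.11 treats unscheduled visits.
4. State that tabulation by CRF visit label continues to apply to scheduled visits.
5. State whether moving to the extension study counts as an ET visit.

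SAP 3.9 and protocol 4.5.2 and 6.4 must also be reconciled with schedule footnote a on which visits follow withdrawal before Day 56.

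The cost is a few sentences, one extra table row, and a smaller n with a wider interval at the affected visits. No new data are needed.
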